## 7 Appendix A

### Motivational messaging (self- vs expert-generated)

**Self:** As part of Charge, we'd like you to write some motivational messages to yourself. These messages will help you stay positive and encouraged. Your next step to get started is to write yourself a few messages to get you started. We will text these to you a few times a week.

**Expert-generated:** As part of Charge, we'll be sending you motivational text messages a few times a week. These messages were written by people who are experts in helping people lose weight, and are meant to help you stay positive and encouraged.

### Texting frequency (daily vs weekly)

**Daily:** Every day, we will text you to ask how you did yesterday with each of your 4 Charge goals. The text will look like this: "Yesterday, did you: eat any red zone foods, drink any sugary drinks, eat 5+ fruits and vegetables, eat any sweet snacks?"

You will reply to this message with your answers to each yes/no question - like this:

"y, y, y, n"

After we get your reply, we'll send you personalized feedback and some tips/ideas about how to reach your goals. Taking a few seconds to reply to us every day helps us keep track of your progress over time – by doing that, we can give you the most personalized and helpful feedback.

**Weekly:** Every week, we will text you to ask how you did with each of your 4 Charge goals. The text will look like this: "Last week, how many days did you: eat any red zone foods, drink any sugary drinks, eat 5+ fruits and vegetables, eat any sweet snacks?"

You will reply to this message with your answers to each yes/no question - like this:

"2, 3, 2, 1"

After we get your reply, we'll send you personalized feedback and some tips/ideas about how to reach your goals. Taking a few seconds to reply to us every week helps us keep track of your progress over time - by doing that, we can give you the most personalized and helpful feedback.

### Reminders (one vs multiple)

**One:** If you don't reply to the first text we send you each [day/week], we will text you one more time to remind you to track your progress. We recommend replying to the first text we send you, so you get it out of the way!

**Multiple:** If you don't reply to the first text we send you each [day/week], we will text you a few more times over the [day/week] to remind you to track your progress. We recommend replying to the first text we send you, so you get it out of the way!

### Feedback type (summary score vs individual goal)

**Summary score:** When we send you feedback every [day/week] we will send one number, an overall score, that considers how you're doing on all of your goals.

**Individual goal:** When we send you feedback every [day/week], we will give you feedback on specific goals. You may not get feedback on how you're doing on every one of your goals individually, but we'll send you smart feedback based on how you're doing over time.

### Comparison unit (self vs group)

**Self:** The feedback we send you each [day/week] will take into account how you've been doing. The more [days/weeks] you track your goals, the better our feedback will be. For example, we may say "You've been getting better at meeting all your goals!" or "Looks like your progress is slowing on each of your goals".

**Group:** The feedback we send you each [day/week] will take into account how you've been doing compared to other people in Charge. For example, we may say, "Only a quarter of Charge participants are doing better than you are" or "Your scores have placed you in the top 10% of program participants".

Condition	Frequency	Motivational Messaging	Reminders	Feedback Type	Comparison Unit
1	Weekly	Self-generated	One	Summary Score	Self
2	Weekly	Self-generated	One	Summary Score	Group
3	Weekly	Self-generated	One	Individual Goal	Self
4	Weekly	Self-generated	One	Individual Goal	Group
5	Weekly	Self-generated	Multiple	Summary Score	Self
6	Weekly	Self-generated	Multiple	Summary Score	Group
7	Weekly	Self-generated	Multiple	Individual Goal	Self
8	Weekly	Self-generated	Multiple	Individual Goal	Group
9	Weekly	Expert-generated	One	Summary Score	Self
10	Weekly	Expert-generated	One	Summary Score	Group
11	Weekly	Expert-generated	One	Individual Goal	Self
12	Weekly	Expert-generated	One	Individual Goal	Group
13	Weekly	Expert-generated	Multiple	Summary Score	Self
14	Weekly	Expert-generated	Multiple	Summary Score	Group
15	Weekly	Expert-generated	Multiple	Individual Goal	Self
16	Weekly	Expert-generated	Multiple	Individual Goal	Group
17	Daily	Self-generated	One	Summary Score	Self
18	Daily	Self-generated	One	Summary Score	Group
19	Daily	Self-generated	One	Individual Goal	Self
20	Daily	Self-generated	One	Individual Goal	Group
21	Daily	Self-generated	Multiple	Summary Score	Self
22	Daily	Self-generated	Multiple	Summary Score	Group
23	Daily	Self-generated	Multiple	Individual Goal	Self
24	Daily	Self-generated	Multiple	Individual Goal	Group
25	Daily	Expert-generated	One	Summary Score	Self
26	Daily	Expert-generated	One	Summary Score	Group
27	Daily	Expert-generated	One	Individual Goal	Self
28	Daily	Expert-generated	One	Individual Goal	Group
29	Daily	Expert-generated	Multiple	Summary Score	Self
30	Daily	Expert-generated	Multiple	Summary Score	Group
31	Daily	Expert-generated	Multiple	Individual Goal	Self
32	Daily	Expert-generated	Multiple	Individual Goal	Group

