## **7. Deception**

Deception will not be used in the present study.

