## 8 Appendix B

**\*Description of Track:** Track was a 12-month weight loss intervention delivered between 2013-2015 that utilized the iOTA framework. Similar to Charge, participants (n= 175 in the intervention arm) were asked to change 4 weight-related behaviors at a time and to report their progress via text message (or automated phone calls) every week. In Track, each participant was assigned 4 goals to track at a time, in 8 week cycles. So some people tracked sugary drinks for the first Cycle (weeks 1-8) and some people tracked it in a different cycle, later in the study. We have self-

monitoring data for 175 participants for 1 year on the same goals as we are assigning in Charge. Track participants were patients at Piedmont Health with obesity and at least 1 obesity-related co-morbidity.

In the **summary score + group comparison** condition (in both self-monitoring conditions), we'll calculate an average score across all 4 goals a participant is tracking each day or week.

We will create a score from the **\*same 4 goals\*** as the participant has using the **\*mean score of each goal\*** for all participants who tracked it the **same cycle week** as the participant. This would mean we could include everyone who ever tracked "No Sugary Drinks" - whether they track it in Cycle 1, 3, or 5. We'd match the score to their cycle week - so if a Charge participant is in the 4th week of Cycle 2, they'd be compared to Track participants who ever tracked "No Sugary Drinks" in the 4th week of any cycle.

We will calculate the following variables to use as referent data:

For the people who get a summary score:

- a. Average summary score for each week (All participants, all goals)
- b. % of people who get each summary score for each week
- c. Mode for each summary score each week
- d. Median for each summary score for each week

For people who get feedback on specific goals:

- a) the average score *for each goal* each week
- b) The percent of people who got each score for each goal each week
- c) the mode for each individual goal each week
- d) the median for each goal score for each week.

**This allows us to analyze the data differently to provide feedback variety - we can tell people their percentile (you're in the top 10%!) or how they're doing compared to most other people, or how they are doing compared to the group's average.**

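### Group-level feedback names other Charge participants as the comparator, but the reference scores come from an earlier trial, Track; the wording, the component definition and the no-deception statement need reconciling

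*Combined protocol and SAP*

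**What the plan says.** SAP Section 3.4 lists performance comparison as one of five primary predictors, with self as the default level and others (group) as the comparator level. It sends the reader to Appendix A for the detailed description.

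Appendix A, in text addressed to the participant, says that Group feedback "will take into account how you've been doing compared to other people in Charge". Its two examples are "Only a quarter of Charge participants are doing better than you are" and "Your scores have placed you in the top 10% of program participants".

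Appendix B describes how the comparison is computed. It introduces Track, an earlier 12-month iOTA trial run in 2013-2015 with 175 participants in its intervention arm. They were patients of one health system with obesity and at least one related co-morbidity, and they reported every week. Participants in Charge are matched on goal and cycle week, and "they'd be compared to Track participants who ever tracked" the same goal in that week of any cycle. The appendix then lists the reference statistics (average, distribution, mode and median by week), both for summary-score feedback and for feedback on specific goals. It says that they will be used to tell people their percentile.

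Protocol Section 7 says: "Deception will not be used in the present study". Section 8 anticipates no need for debriefing.

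**The concern.** The two SAP appendices give different answers to the question of whom the participant is compared with. Appendix A tells the participant it is their fellow participants; Appendix B takes another study's patients. Both cannot be right, and if Appendix B is what was built, the statement made to participants is untrue as to the comparator.

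Two things are at stake. The first is truthfulness, since the protocol states without qualification that there is no deception. The second is what the trial may conclude about the component. SAP Section 4 uses the 6-month effect of each component to decide which level enters the final package. If the Group level is chosen or dropped, readers relying on Appendix A will take that as evidence about comparison with current peers, when the messages rested on a historical cohort recruited under different criteria.

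**Working it through.** No figure in the plan decides this point, so the check is mainly a comparison of texts.

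**Step 1: the comparator named and the comparator used.**

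| Item | Named to participants (Appendix A) | Used in the calculation (Appendix B) |
|---|---|---|
| Who | Other people in Charge | Track participants with the same goal and cycle week |
| When | Current programme | 2013-2015 |
| Population | Charge: BMI above 25 (SAP Section 2.1) | Obesity plus at least one co-morbidity |
| Reporting | Daily or weekly, by condition | Weekly |

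Appendix B names no Charge data as a source for the reference. The sentence in Appendix A that identifies the comparator is unqualified; only the sample messages are introduced as things the system may say. So the conflict does not depend on the examples.

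**Step 2: how many participants it covers.** The condition table gives the Group level in every even-numbered condition: 32 / 2 = 16. Appendix B covers both texting frequencies and both feedback types, so all 16 use the Track reference. With 14 per condition (SAP Section 2.3), 16 x 14 = 224 of 32 x 14 = 448. This agrees with the plan's own 224 per component level.

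**Step 3: could the stated rank also be numerically wrong?** The documents give no score distribution for Track or Charge, so this cannot be computed. For scale only, assume normal scores with equal SD in the two cohorts and let s be the Charge mean minus the Track mean in SD units. Then:

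- share of Charge above Track's 90th percentile = 1 - Phi(1.2816 - s)
- share of Charge above Track's 75th percentile = 1 - Phi(0.6745 - s)

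| s (assumed) | Above Track's 90th | Above Track's 75th |
|---|---|---|
| -0.50 | 3.7% | 12.0% |
| -0.25 | 6.3% | 17.8% |
| 0 | 10.0% | 25.0% |
| +0.25 | 15.1% | 33.6% |
| +0.50 | 21.7% | 43.1% |

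Nothing in the documents says which sign s has, or that it differs from zero. At s = 0 the rank would be right on average, but the comparator would still be misnamed.

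**Step 4: effect on the sample size.** None. Changing the wording or the definition leaves 282, 403 and 448 as they are.

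**The case against.** The strongest reply has four parts.

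- **The broader definitions fit Track.** The protocol speaks only of comparison with a group of people, and SAP Section 3.4 of others (group). Appendix B discloses the Track source openly. This is true, and it limits the conflict to Appendix A. But Section 3.4 makes Appendix A the detailed definition, and Appendix A is the text addressed to participants.
- **The documents do not show what was sent.** The sample messages are examples, Appendix B is worded partly in the conditional, and the consent text is not available here. This stands: the finding is about the plan as written. Whether it amounts to deception in the formal sense is for the ethics board.
- **Randomisation protects the contrast.** This also stands. Self versus Group is a fair comparison of the messages as delivered. A reader might infer that the effect is biased, or that the frequency-by-comparison interaction is distorted. The documents do not support this: the interaction estimates what the intervention, as built, does at each texting frequency. What suffers is the label.
- **Using Track is sensible.** Early enrollees would have few Charge peers with the same goal and cycle week. Agreed; the fault is in naming the comparator, not in choosing it.

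Two further inferences are tempting. One is that daily participants' single-day scores are ranked against weekly scores. Appendix B says that it will "calculate an average score across all 4 goals a participant is tracking each day or week" and lists only weekly reference statistics, but never says that a one-day score is placed on the weekly distribution. The protocol says that feedback considers short- and long-term progress. The other is that the entry "Average summary score for each week (All participants, all goals" contradicts the same-four-goals rule. It can be read as everyone who tracked, averaged over the four goals. Both are under-specified and call for clarification; neither is a demonstrated error.

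**Conclusion.** The point holds as a contradiction within the plan. Appendix A, Appendix B and Protocol Section 7 cannot all stand as written. The misnamed comparator applies to half the conditions (224 of 448 planned participants). The Group effect should be read as the effect of comparison with an external historical cohort presented as fellow participants, not of comparison with Charge peers.

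This rests on Appendix B describing the algorithm that was used and Appendix A the wording that was used. A reader might go further and conclude that the percentiles themselves were wrong, or inflated. The documents give no score data to support either conclusion. The 4% to 22% range for Track's top 10% is an illustration under assumed shifts in both directions.

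**What to change.** 1. For anyone still to be enrolled, including the up to 5000 participants of Phase II, reword the Appendix A text and messages to name the real comparator, for example *people in an earlier program like Charge*.
2. Define the Group level in SAP Section 3.4 and Appendix A as comparison with the Track reference.
3. Bring Protocol Sections 7 and 8 into line with the wording used, and put the question to the ethics board.
4. For participants already treated, report which reference group and which wording they received. The SAP dataset is dated October 2019, so rewording may come too late for the in-person cohort.
5. As clarifications in Appendix B, state how a daily participant's score is placed on the weekly Track reference, and whether the all-goals entry means the same four goals.

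The cost is a change of message text and some SAP wording; the sample size and model are unaffected. The downside is that later participants would see different wording from earlier ones. Phase II is meant to deliver the same intervention, so the difference must be noted by phase when results are interpreted.

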## 8 Appendix B

**\*Description of Track:** Track was a 12-month weight loss intervention delivered between 2013-2015 that utilized the iOTA framework. Similar to Charge, participants (n= 175 in the intervention arm) were asked to change 4 weight-related behaviors at a time and to report their progress via text message (or automated phone calls) every week. In Track, each participant was assigned 4 goals to track at a time, in 8 week cycles. So some people tracked sugary drinks for the first Cycle (weeks 1-8) and some people tracked it in a different cycle, later in the study. We have self-

monitoring data for 175 participants for 1 year on the same goals as we are assigning in Charge. Track participants were patients at Piedmont Health with obesity and at least 1 obesity-related co-morbidity.

In the **summary score + group comparison** condition (in both self-monitoring conditions), we'll calculate an average score across all 4 goals a participant is tracking each day or week.

We will create a score from the **\*same 4 goals\*** as the participant has using the **\*mean score of each goal\*** for all participants who tracked it the **same cycle week** as the participant. This would mean we could include everyone who ever tracked "No Sugary Drinks" - whether they track it in Cycle 1, 3, or 5. We'd match the score to their cycle week - so if a Charge participant is in the 4th week of Cycle 2, they'd be compared to Track participants who ever tracked "No Sugary Drinks" in the 4th week of any cycle.

We will calculate the following variables to use as referent data:

For the people who get a summary score:

- a. Average summary score for each week (All participants, all goals)
- b. % of people who get each summary score for each week
- c. Mode for each summary score each week
- d. Median for each summary score for each week

For people who get feedback on specific goals:

- a) the average score *for each goal* each week
- b) The percent of people who got each score for each goal each week
- c) the mode for each individual goal each week
- d) the median for each goal score for each week.

**This allows us to analyze the data differently to provide feedback variety - we can tell people their percentile (you're in the top 10%!) or how they're doing compared to most other people, or how they are doing compared to the group's average.**
